3.3.2 Exclusion Criteria

1) Target Disease Exceptions

- a) Subjects with untreated CNS metastases. Subjects are eligible if CNS metastases have been adequately treated and have neurologically returned to baseline (except for residual signs or symptoms related to the CNS treatment) for at least 2 weeks. In addition, subjects must be either off corticosteroids or on a stable or decreasing dose of prednisone 10 mg daily (or equivalent) for at least 2 weeks. Please note: For SCCHN subjects only, cases including base of skull lesions without definitive evidence of dural or brain parenchymal involvement, should be discussed with the Medical Monitor.
- b) Participation in any prior clinical study with ipilimumab or with nivolumab, including subjects in comparator arms (including CA209651 and CA209714), in which OS is listed as the primary or co-primary endpoint and which has not completed analysis based on the primary endpoint.

- c) SCCHN subjects only: Histologically confirmed recurrent or metastatic carcinoma of the nasopharynx, and the skin and salivary gland or non-squamous histologies are not allowed.
- d) Subjects with carcinomatous meningitis.

2) Medical History and Concurrent Diseases

- a) Subjects with previous malignancies (except non-MEL skin cancers, and the following in situ cancers: bladder, gastric, colon, esophageal endometrial, cervical/dysplasia, MEL, or breast) unless a complete remission was achieved at least 2 years prior to study entry AND no additional therapy is required during the study period.
- b) Subjects with an active, known, or suspected autoimmune disease. Subjects with type I diabetes mellitus, hypothyroidism only requiring hormone replacement, skin disorders (such as vitiligo, psoriasis, or alopecia) not requiring systemic treatment, or conditions not expected to recur in the absence of an external trigger are permitted to enroll.
- c) A known or underlying medical condition that, in the opinion of the investigator or Sponsor, could make the administration of study drug hazardous to the subjects (such as ongoing interstitial pneumonitis), or could adversely affect the ability of the subject to comply with or tolerate study. Not applicable starting with Protocol Amendment 13 and all subsequent amendments.
- d) Uncontrolled or significant cardiovascular disease including, but not limited to any of the following:
 - i) Myocardial infarction or stroke/transient ischemic attack within the past 6 months
 - ii) Uncontrolled angina within the past 3 months
 - iii) Any history of clinically significant arrhythmias (such as ventricular tachycardia, ventricular fibrillation or torsades de pointes)
 - iv) QTc prolongation > 480 msec
 - v) History of other clinically significant heart disease (ie, cardiomyopathy, congestive heart failure with New York Heart Association functional classification 3 to 4, pericarditis, significant pericardial effusion)
 - vi) Requirement of daily supplemental oxygen therapy
 - vii) History of myocarditis
- e) Known history of positive test for human immunodeficiency virus (HIV) or known acquired immunodeficiency syndrome. No HIV testing is required during screening. NOTE: Testing for HIV must be performed at study sites where mandated locally.
 - i) Subjects with positive hepatitis C antibody and negative quantitative hepatitis C by PCR are eligible. Not applicable starting with Protocol Amendment 13 and all subsequent amendments.
 - ii) Subjects with a history of resolved hepatitis A virus infection are eligible. Not applicable starting with Protocol Amendment 13 and all subsequent amendments.
- f) Evidence of active infection ≤ 7 days prior to initiation of study drug therapy (does not apply to viral infections that are presumed to be associated with the underlying tumor type required for study entry). Not applicable starting with Protocol Amendment 13 and all subsequent amendments.
- g) Any serious or uncontrolled medical disorders.

- h) Any major surgery within 4 weeks of study drug administration.
- i) Subjects who are unable to undergo venipuncture and/or to tolerate venous access. Not applicable starting with Protocol Amendment 13 and all subsequent amendments.
- j) Any other sound medical, psychiatric and/or social reason as determined by the investigator. Not applicable starting with Protocol Amendment 13 and all subsequent amendments.
- k) All toxicities attributed to systemic prior anti-cancer therapy other than alopecia and fatigue must have resolved to Grade 1 (National Cancer Institute [NCI] Common Terminology Criteria for Adverse Events [CTCAE] version 4.03 [v4.03]) or baseline before administration of study drug. Subjects with toxicities attributed to systemic prior anti-cancer therapy, that are not expected to resolve, and that result in long lasting sequelae, such as neuropathy after platinum-based therapy, are permitted to enroll.
- l) Subjects with a condition requiring systemic treatment with either corticosteroids (prednisone > 10 mg daily or equivalent) or other immunosuppressive medications within 14 days of start of study drug (or randomization, for the SCCHN Randomized Cohorts [Part 3] and the Signal Detection in SCCHN with Lirilumab, Nivolumab, and Ipilimumab Combination [Part 5]). Inhaled or topical steroids, and adrenal replacement steroid doses prednisone > 10 mg daily or equivalent, are permitted in the absence of active autoimmune disease.

3) Prohibited Prior Treatments and/or Therapies

- a) Prior treatment with an anti-KIR antibody or an anti-PD-1, anti-PD-L1, anti-PD-L2, or anti-CTLA-4 antibody, or any other antibody or drug specifically targeting T-cell co-stimulation or checkpoint pathways except as noted below.
- b) Prior treatment regimens with any immune cell modulating antibody such as anti-CD137 and anti-OX40. However, prior anti-CTLA-4 therapy is allowed if the last dose is 101 days or more from the first dose of study drug. Not applicable starting with Amendment 13 and all subsequent amendments.
- c) Exposure to any other investigational drug within 4 weeks prior to the first dose of study drug.
- d) Treatment with any anti-cancer therapy, chemotherapy, radiation therapy, biologics for cancer, or investigational therapy within 28 days of first administration of study drug (subjects with prior radiation, cytotoxic or investigational products < 4 weeks prior to treatment might be eligible after discussion between investigator and Sponsor, if toxicities from the prior treatment have been resolved to Grade 1 [NCI CTCAE v4.03]).
- e) Prior focal palliative radiotherapy within 2 weeks prior to the first dose of study administration.
- f) Use of non-oncology vaccines containing live virus for prevention of infectious diseases within 4 weeks prior to study drug. The use of the inactivated seasonal influenza vaccine (Fluzone[®]) is allowed. Not applicable starting with Protocol Amendment 13 and all subsequent amendments.
- g) Use of growth factors, including, but not limited to, granulocyte-colony stimulating factor, granulocyte macrophage-colony stimulating factor, or erythropoietin within 4 weeks prior to the first dose of study drug. Not applicable starting with Protocol Amendment 13 and all subsequent amendments.

- h) Use of packed red blood cells or platelet transfusion within 2 weeks prior to the first dose of study drug. Not applicable starting with Protocol Amendment 13 and all subsequent amendments.
- i) Inhaled or topical steroids and adrenal replacement doses prednisone > 10 mg/day or equivalent are permitted in the absence of active autoimmune disease.
- j) Use of receptor activator of nuclear factor kappa-B ligand inhibitors within 10 weeks prior to the first dose of study drug. Not applicable starting with Protocol Amendment 13 and all subsequent amendments.
- k) Use of bisphosphonates within 4 weeks prior to the first dose of study drug. Not applicable starting with Protocol Amendment 13 and all subsequent amendments.
- l) Use of any medicinal herbal preparations within 2 weeks prior to the first dose of study drug. Not applicable starting with Protocol Amendment 13 and all subsequent amendments.

4) Physical and Laboratory Test Findings

- a) Positive tests for HIV antibody (may obtain additional testing or substitute testing per institutional guidelines to rule out infection) or known acquired immunodeficiency syndrome.
- b) Any positive test result for hepatitis B virus or hepatitis C virus indicating presence of the virus, eg, HBsAg (Australia antigen) positive, or hepatitis C antibody (anti-HCV) positive (except if HCV-RNA negative).
 - i) Subjects with positive hepatitis C antibody and negative quantitative hepatitis C by PCR are eligible. Not applicable starting with Protocol Amendment 13 and all subsequent amendments.
 - ii) Subjects with a history resolved hepatitis A virus infection are eligible. Not applicable starting with Protocol Amendment 13 and all subsequent amendments.
- c) Any Grade 4 laboratory abnormalities.

5) Allergies and Adverse Drug Reaction

- a) History of allergy or hypersensitivity to study drug components (eg, history of severe hypersensitivity reactions to drugs formulated with polysorbate 80).

6) Sex and Reproductive Status

- a) Women who are pregnant or are breastfeeding.

7) Other Exclusion Criteria

- a) Prisoners or subjects who are involuntarily incarcerated.
- b) Subjects who are compulsorily detained for treatment of either a psychiatric or physical (eg, infectious disease) illness.

Eligibility criteria for this study have been carefully considered to ensure the safety of the study subjects and to ensure that the results of the study can be used. It is imperative that subjects fully meet all eligibility criteria.

3.3.3 Women of Childbearing Potential

A WOCBP is defined as any female who has experienced menarche and who has not undergone surgical sterilization (hysterectomy or bilateral oophorectomy) or is **not** postmenopausal.

Menopause is defined clinically as 12 months of amenorrhea in a woman over age 45 in the absence of other biological or physiological causes. In addition, women under the age of 55 must have a documented serum follicle-stimulating hormone (FSH) level > 40 mIU/mL to confirm menopause.

Females treated with HRT are likely to have artificially suppressed FSH levels and may require a washout period in order to obtain a physiologic FSH level. The duration of the washout period is a function of the type of HRT used. The durations of the washout periods below are suggested guidelines and the investigators should use their judgement in checking serum FSH levels. If the serum FSH level is > 40 mIU/mL at any time during the washout period, the woman can be considered postmenopausal.

- 1 week minimum for vaginal hormonal products (ie, rings, creams, and gels)
- 4 week minimum for transdermal products
- 8 week minimum for oral products

Other parenteral products may require washout periods as long as 6 months.

3.4 Concomitant Treatments

3.4.1 Prohibited and/or Restricted Treatments

The following medications are prohibited during the study (unless utilized to treat a drug-related AE):

- Immunosuppressive agents (except as stated in Section 3.4.3).
- Immunosuppressive doses of systemic corticosteroids (except as stated in Sections 3.4.2 and 3.4.3)
- Any concurrent anti-neoplastic therapy (ie, chemotherapy, hormonal therapy, immunotherapy, extensive, non-palliative radiation therapy, or standard or investigational agents).

3.4.2 Other Restrictions and Precautions

Subjects with a condition requiring systemic treatment with either corticosteroids (prednisone > 10 mg daily or equivalent) or other immunosuppressive medications within 14 days of study drug assignment or randomization are excluded. Inhaled or topical steroids, and adrenal replacement steroid doses prednisone > 10 mg daily or equivalent, are permitted in the absence of active autoimmune disease.

3.4.3 Permitted Therapy

Subjects are permitted the use of topical, ocular, intra-articular, intra-nasal, and inhalational corticosteroids (with minimal systemic absorption). Adrenal replacement steroid doses prednisone > 10 mg daily are permitted. A brief (< 3 weeks) course of corticosteroids for prophylaxis (eg, contrast dye allergy) or for treatment of non-autoimmune conditions (eg, delayed-type hypersensitivity reaction caused by a contact allergen) is permitted.

Subjects may continue to receive HRT.

Regular concomitant use of bisphosphonates and receptor activator of nuclear factor kappa B ligand (RANK-L) inhibitors for prevention or reduction of skeletal-related events in subjects with bone metastases is allowed if initiated prior to first dose of study drug. Prior palliative radiotherapy must have been completed at least 2 weeks prior to randomization

Prior palliative radiotherapy must have been completed at least 4 weeks prior to randomization for cases of radiotherapy to the head and neck, and completed within 2 weeks prior to randomization for radiotherapy to other sites. On-study palliative radiotherapy is only allowed for treatment of painful bone lesions. Palliative surgical resection of tumor sites is not permitted. Subjects requiring palliative radiotherapy should be evaluated for objective evidence of disease progression prior to the initiation of such therapy, particularly if the most recent tumor assessment was more than 4 weeks prior to the start of local therapy. If progression per RECIST v1.1 is identified on any tumor assessments prior to the initiation of palliative local therapy, then subjects must discontinue study drug.

The potential for overlapping toxicities with radiotherapy and nivolumab/lirilumab; nivolumab/ipilimumab/lirilumab and nivolumab/ipilimumab currently is not known; however, anecdotal data suggest these combinations may be tolerable. As concurrent radiotherapy and the IO combination therapy have not been formally evaluated, in cases where palliative radiotherapy is required for a tumor lesion, then study drug should be withheld for at least 1 week before, during, and 1 week after radiation. Subjects should be closely monitored for any potential toxicity during and after receiving radiotherapy, and AEs should resolve to Grade \leq 1 prior to resuming nivolumab or nivolumab plus ipilimumab.

Palliative and supportive care for disease related symptoms may be offered to all subjects on the study; for subjects in the Dose Escalation and Cohort Expansion (Part 1; completed), this must be after the DLT evaluation period. Limited radiation therapy or surgery to control isolated lesions is permitted for subjects who have investigator-assessed clinical benefit (eg, irSD or irPR) following consultation with the BMS Medical Monitor. Subjects should not receive study drug during radiation or surgery.

3.5 Discontinuation of Subjects from Treatment

Subjects MUST discontinue investigational product (and non-investigational product at the discretion of the investigator) for any of the following reasons:

- Withdrawal of informed consent (subject's decision to withdraw for any reason)
- Any clinical AE, laboratory abnormality, clinical deterioration, or concurrent illness that in the opinion of the investigator indicates that continued participation in the study is not in the best interest of the subject
- Pregnancy
- Termination of the study by BMS
- Loss of ability to freely provide consent through imprisonment or involuntary incarceration for treatment of either a psychiatric or physical (eg, infectious disease) illness

- Documented and confirmed irPD as defined by irRECIST for the Dose Escalation and Cohort Expansion (Part 1; completed) and the SCCHN Cohort Expansion (Part 2; completed) (see [Appendix 2](#)).
- Documented PD for the SCCHN Randomized Cohorts (Part 3), and the Signal Detection in SCCHN with Lirilumab, Nivolumab, and Ipilimumab Combination (Part 5) as defined by RECIST v1.1 (see [Appendix 3](#)).
- Documented and confirmed irCR as defined by irRECIST for the Dose Escalation and Cohort Expansion (Part 1; completed) and the SCCHN Cohort Expansion (Part 2; completed) (see [Appendix 2](#)).
- Documented and confirmed CR for the Signal Detection in SCCHN with Lirilumab, Nivolumab, and Ipilimumab Combination (Part 5) as defined by RECIST v1.1 (see [Appendix 3](#)).
- Discretion of the investigator
- Inability to comply with the protocol requirements
- Protocol defined reasons for discontinuation (see [Section 4.9.5](#))
- Maximum treatment duration of up to a maximum of 2 years; 12 cycles in Parts 1, 2, and 3 or 8 cycles in Part 5.

In the case of pregnancy, the investigator must immediately notify the Sponsor or designee of this event. In most cases, the study drug will be permanently discontinued in an appropriate manner (eg, dose tapering if necessary for subject safety). Please contact the Sponsor or designee within 24 hours of awareness of the pregnancy. If the investigator determines a possible favorable benefit/risk ratio that warrants continuation of study drug, a discussion between the investigator and the Sponsor or designee must occur.

All subjects who discontinue should comply with protocol specified follow-up procedures as outlined in [Section 5.1](#). The only exception to this requirement is when a subject withdraws consent for all study procedures or loses the ability to consent freely (ie, is imprisoned or involuntarily incarcerated for the treatment of either a psychiatric or physical illness).

If study drug is discontinued prior to the subject's completion of the study, the reason for the discontinuation must be documented in the subject's medical records and entered on the appropriate CRF page.

3.5.1 Treatment Beyond Disease Progression

With Revised Protocol 12, no additional subjects are permitted to enter Treatment Beyond Disease progression. At the time of initial progressive disease, subjects will be required to discontinue study treatment and enter clinical follow-up.

As defined in [Section 5.4](#); treatment related decisions will be governed by irRECIST based response assessments. The proposed irRECIST criteria allows for continued study therapy beyond initial RECIST v1.1 defined PD and will only be permitted provided the following criteria are met:

- Clinical benefit as assessed by the investigator
- Disease progression is not rapid

- Continues to meet all other study protocol eligibility criteria
- Tolerance of study drug
- Stable performance status
- Treatment beyond progression will not delay an imminent intervention to prevent serious complications of disease progression (eg, CNS metastases)
- Subjects have provided written informed consent prior to receiving additional treatment with their assigned treatment.

In the combination setting, subjects who meet criteria may continue on lirilumab and nivolumab in combination but may not continue on 1 treatment or the other alone.

For the SCCHN Randomized Cohorts (Part 3), and the Signal Detection in SCCHN with Lirilumab, Nivolumab, and Ipilimumab Combination (Part 5), decisions related to treatment beyond progression will be made with RECIST v1.1.

Subjects should discontinue study therapy upon further evidence of further progression, defined as an additional 10% or greater increase in tumor burden volume from time of initial progression (including all target lesions and new measurable lesions).

New lesions are considered measureable at the time of initial progression if the longest diameter is at least 10 mm (except for pathological lymph nodes which must have a short axis of at least 15 mm). Any new lesion considered nonmeasureable at the time of initial progression may become measureable and therefore included in the tumor burden if the longest diameter increases to at least 10 mm (except for pathological lymph nodes, which must have a short axis of at least 15 mm).

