Following each treatment cycle (for all assigned treatments), the decision to treat a subject with additional cycles of study therapy will be based on tumor assessment (evaluation performed between Days 49 and 56 and completed before the first dose in the next 8 week cycle for all study parts except the Signal Detection in SCCHN with Lirilumab, Nivolumab, and Ipilimumab Combination [Part 5], which is performed Q8W and completed before study therapy is continued. Treatment decisions related to subject management will be based exclusively on irRECIST for the Dose Escalation and Cohort Expansion (Part 1; completed) and the SCCHN Cohort Expansion (Part 2; completed) (see protocol body [Section 1.4.14](#) for the rationale and [Appendix 2](#) for definitions); with Amendment 13, all other study parts will use only RECIST v1.1 (see protocol body [Sections 3.1.3, 3.1.4, 3.1.5, and 3.1.6](#) for details).

Subjects will generally be allowed to continue study therapy until the first occurrence of any of the following:

- a) Achievement of irCR-confirmed (the Dose Escalation and Cohort Expansion [Part 1; completed] and the SCCHN Cohort Expansion [Part 2; completed]) or CR-confirmed the Signal Detection in SCCHN with Lirilumab, Nivolumab, and Ipilimumab Combination [Part 5]).
- b) Completion of a maximum of up to 2 years of the study treatment; 12 cycles in Parts 1, 2 and 3, and 8 cycles in Part 5.
- c) irPD (the Dose Escalation and Cohort Expansion [Part 1; completed] and the SCCHN Cohort Expansion [Part 2; completed]) or PD confirmed or unconfirmed (the SCCHN Randomized Cohorts [Part 3], and the Signal Detection in SCCHN with Lirilumab, Nivolumab, and Ipilimumab Combination [Part 5]).
- d) Clinical deterioration suggesting that no further benefit from treatment is likely.
- e) Intolerability to therapy.
- f) Meeting criteria for discontinuation of study therapy as outlined in protocol body [Sections 3.5 and 4.9.5](#).

For all study parts, the subjects listed above will enter the clinical follow-up period, with visits scheduled on Days 30, 60, 100, and 150 to monitor for adverse events (AE)s.

Survival follow-up is no longer required with Revised Protocol 12 and no further visits should be conducted.

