1.4.14 Rationale for Use of Immune-Related Response Criteria

NOTE: This section will only be applicable for the Dose Escalation and Cohort Expansion (Part 1; completed) and the SCCHN Cohort Expansion (Part 2; completed) of this study.

Clinical evidence suggests that some subjects treated with immune-modulating agents may have PD before demonstrating clinical response.³² The mechanism behind this finding is unknown but may include an early inflammatory and immune cell trafficking phase that can be misinterpreted as tumor growth or as the kinetics of fast tumor growth vs initial slow anti-tumor activity. What is clear is that the use of standard response criteria has the potential of removing subjects from study too early. In the ipilimumab study, approximately 10% of subjects who were deriving clinical benefit had evidence of disease progression as determined by modified World Health Organization criteria.²² Therefore, exploratory response criteria modified from Response Evaluation Criteria in Solid Tumors (RECIST) have been developed to take into account an immune-mediated pattern of objective response (irRECIST).⁹

[Appendix 2](#) lists irRECIST criteria. The 2 main modifications are that disease progression will require confirmation at least 4 weeks following the restaging scan and that the appearance of new lesions may not be considered disease progression. In this protocol, irRECIST will be used for study conduct. Statistical analyses will be primarily based on RECIST version 1.1 (v1.1) criteria (see [Appendix 3](#)).

With Amendment 13 (Revised Protocol 10), additional study parts will use RECIST v1.1 instead of irRECIST.

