3.1.1 The Dose Escalation and Cohort Expansion (Part 1; Completed)

Subjects in the dose escalation and cohort expansion periods of the Dose Escalation and Cohort Expansion (Part 1) will complete up to 4 study periods: screening, treatment, clinical follow-up, and survival follow-up. **Screening** (up to 28 days). **Treatment** (up to maximum of 2 years). **Clinical follow-up** (150 days). **Survival follow-up** (up to 3 years following the first dose of study drug). Survival follow-up is no longer applicable with Revised Protocol 12 and no further visits should be conducted. With revised protocol 12, the total time on study for any individual subject will not exceed approximately 2.5 years.

The treatment period will last up to twelve 8-week treatment cycles. For subjects receiving lirilumab and nivolumab combination therapy in the Dose Escalation and Cohort Expansion (Part 1), each treatment cycle is composed of 4 doses of nivolumab and 2 doses of lirilumab. Nivolumab will be administered on Days 1, 15, 29, and 43 of each treatment cycle, and lirilumab will be administered on Days 1 and 29 of each treatment cycle.

[figure not shown]
Following each treatment cycle (for all assigned treatments), the decision to treat a subject with additional cycles of study therapy will be based on tumor assessment (evaluation performed between Days 49 and 56 and completed before the first dose in the next cycle). Treatment decisions related to subject management will be based exclusively on irRECIST for the Dose Escalation and Cohort Expansion (Part 1) (see [Section 1.4.14](#) for the rationale and [Appendix 2](#) for definitions).

For the Dose Escalation and Cohort Expansion (Part 1), subjects with an overall response of irPD-unconfirmed, irSD, irPR, or irCR-unconfirmed at the end of a given cycle will continue to the next treatment cycle. Subjects will generally be allowed to continue study therapy until the first occurrence of any of the following: 1) achievement of irCR-confirmed; 2) completion of 12 cycles; 3) confirmation of irPD; 4) clinical deterioration suggesting that no further benefit from treatment is likely; 5) intolerability to therapy; or 6) meeting criteria for discontinuation of study therapy as outlined in [Sections 3.5](#) and [4.9.5](#).

The subjects listed above will enter the clinical follow-up period, with visits scheduled on Days 30, 60, 100, and 150 to monitor for AEs.

A study schematic is presented below in [Figure 3.1.1-1](#).

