Following each treatment cycle (for all assigned treatments), the decision to treat a subject with additional cycles of study therapy will be based on tumor assessment (evaluation performed between Days 49 and 56 and completed before the first dose in the next cycle). Treatment decisions related to subject management will be based exclusively on irRECIST for the SCCHN Cohort Expansion (Part 2) (see Section 1.4.14 for the rationale and Appendix 2 for definitions). For the SCCHN Cohort Expansion (Part 2), subjects with an overall response of irPD-unconfirmed, irSD, irPR, or irCR-unconfirmed at the end of a given cycle will continue to the next treatment cycle. Subjects will generally be allowed to continue study therapy until the first occurrence of any of the following: 1) achievement of irCR-confirmed; 2) completion of 12 cycles; 3) confirmation of irPD; 4) clinical deterioration suggesting that no further benefit from treatment is likely; 5) intolerability to therapy; or 6) meeting criteria for discontinuation of study therapy as outlined in Sections 3.5 and 4.9.5.

The subjects listed above will enter the clinical follow-up period, with visits scheduled on Days 30, 60, 100, and 150 to monitor for AEs.

A study schematic is presented below in Figure 3.1.2-1.

The SCCHN Cohort Expansion (Part 2) of this study closed to enrollment when the SCCHN Randomized Cohorts (Part 3) opened.

Figure 3.1.2-1: Study Period Schematic for Part 2 (Completed)

^a Survival follow-up no longer applicable with Revised Protocol 12

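### Section 3.5.1 stops treatment at first progression while the Part 1 and 2 rules continue it until irPD is confirmed, so an unconfirmed irPD scan leads to contradictory actions

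*Protocol*

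**What the plan says.** **The new rule.** Protocol Section 3.5.1 opens with two sentences tied to Revised Protocol 12. The first says that "no additional subjects are permitted to enter Treatment Beyond Disease progression". The second says: "At the time of initial progressive disease, subjects will be required to discontinue study treatment and enter clinical follow-up". Neither is limited to a study part, and neither names the response criteria.

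**The rest of Section 3.5.1.** The next paragraph was kept. It says that irRECIST governs treatment decisions, and adds: "The proposed irRECIST criteria allows for continued study therapy beyond initial RECIST v1.1 defined PD", subject to listed conditions.

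**Parts 1 and 2.** Section 3.1.1 states: "Treatment decisions related to subject management will be based exclusively on irRECIST for the Dose Escalation and Cohort Expansion (Part 1"; Section 3.1.2 says the same for Part 2. Both sections say that subjects with "irPD-unconfirmed, irSD, irPR, or irCR-unconfirmed at the end of a given cycle will continue to the next treatment cycle", and both give confirmation of irPD as the progression event that ends treatment. SAP Sections 2.1.1 and 2.1.2 repeat this.

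**Mandatory discontinuation list.** Section 3.5 has "Documented and confirmed irPD as defined by irRECIST for the Dose Escalation and Cohort Expansion (Part 1; completed", an item that also covers Part 2. For Parts 3 and 5 it asks only for documented PD by RECIST v1.1.

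**Synopsis item (c).** The stopping event is "irPD (the Dose Escalation and Cohort Expansion [Part 1; completed] and the SCCHN Cohort Expansion [Part 2; completed]) or PD confirmed or unconfirmed". The qualifier is followed by Parts 3 and 5; the Part 1 and 2 entry says nothing about confirmation.

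**Rationale.** Section 1.4.14, which applies only to Parts 1 and 2, says "disease progression will require confirmation at least 4 weeks following the restaging scan".

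**The concern.** The protocol separates the parts deliberately: confirmed irPD for Parts 1 and 2, any documented RECIST v1.1 PD for Parts 3 and 5. The sentence added to Section 3.5.1 removes that distinction, but the sections that create it were not changed. A site with a Part 1 or 2 subject on treatment would find an instruction to stop in one place and an instruction to continue in another, both current.

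Parts 1 and 2 are also the parts that SAP Section 7.1 summarizes; Parts 3 and 5 are listed only. If sites resolved the conflict differently, the summarized exposure and safety data would mix two stopping rules, and either choice would depart from some current section.

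**Working it through.** No sample size, power or error rate is involved. The check sets the passages side by side, counts the doses between the two readings, and traces the effect into the SAP.

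**1. Action by scan result** (subject not already in treatment beyond progression)

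| Scan result | Section 3.5.1, new rule | Sections 3.1.1 and 3.1.2 | Section 3.5 list |
|---|---|---|---|
| Parts 1 and 2: first irPD, unconfirmed | Stop | Continue | No mandatory stop |
| Parts 1 and 2: unequivocal new lesion, tumor burden up by less than 20% | Stop, if RECIST v1.1 is meant | Continue (irSD) | No mandatory stop |
| Parts 1 and 2: confirmed irPD | Stop | Stop | Stop |
| Parts 3 and 5: first RECIST v1.1 PD | Stop | Not applicable (3.1.3 and 3.1.5: stop) | Stop |

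The first row conflicts whether progressive disease in Section 3.5.1 means RECIST v1.1 PD or a first irPD. Only reading it as confirmed irPD would remove the conflict. That does not fit the word initial, or the same section's reference to initial RECIST v1.1 PD.

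The second row depends on the criteria. Appendix 3, Section 3.3 counts an unequivocal new lesion as progression. Appendix 2, Section 3.3 says that new lesions alone are not progression, and its Table 1 gives irSD for a change between −30% and +20%.

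**2. Doses between the two actions**

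The scan falls on Days 49 to 56. In the next cycle, nivolumab is given on Days 1, 15, 29 and 43, and lirilumab on Days 1 and 29 (Sections 3.1.1 and 3.1.2).

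- Earliest confirmation, 28 days after the scan: 49 + 28 − 56 = Day 21, to 56 + 28 − 56 = Day 28, of the next cycle. Doses by then: nivolumab on Days 1 and 15 (2), lirilumab on Day 1 (1).
- Confirmation at the next 8-week scan: 56/14 = 4 nivolumab and 56/28 = 2 lirilumab doses.

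**3. Could anyone be affected?**

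Maximum treatment is 12 × 8 = 96 weeks = 672 days. Counting back from Revised Protocol 12, 08-May-2018 − 672 days = 05-Jul-2016, so a subject first dosed after that date could still have been on treatment, assuming no dosing delays.

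Part 2 closed when Part 3 opened, and Part 3 was added by Amendment 13, dated 12-Dec-2016. The documents do not give the last Part 2 first-dose date. If it were 12-Dec-2016 (an assumption), the subject would be 512 days, or 73 weeks, into treatment at Revised Protocol 12, with about 96 − 73 = 23 weeks left. For first doses before 05-Jul-2016, nothing is left.

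**4. Effect on the analyses**

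- Affected: duration of therapy and cumulative dose, which run to the last dose (SAP 7.4.1); reason for discontinuation (SAP 7.3.1); and the adverse event window, which ends 150 days after the last dose (SAP 7.6).
- Not affected: best overall response, which is cut at initial RECIST v1.1 progression even if treatment goes on (SAP 4.2.1.1), and PFS, which uses the first documented RECIST v1.1 progression (SAP 4.2.1.4). In both conflicting rows RECIST v1.1 progression has been recorded by the scan in question, so later dosing cannot change either endpoint.

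**The case against.** The strongest reply is that the intent is clear. The new rule is dated and repeated: the rationale for Revised Protocol 12 and Section 1 announce the same change and attribute it to the lack of a differential efficacy signal, and Section 1.4.15 is marked as no longer applicable. Section 3.1 also calls Parts 1 and 2 not applicable from Amendment 13 onward.

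Part of this stands. The signposting makes divergent action less likely, and leaving Section 1.4.14 in place is better seen as incomplete updating than as an unreasoned rule. It does not remove the conflict. Sections 3.1.1 and 3.1.2 carry Revised Protocol 12 text on survival follow-up and time on study, so they are current. Section 3.5 still names Parts 1 and 2. Subjects with benefit may stay on treatment until discontinuation criteria are met, and it is those criteria that disagree. The protocol gives no order of precedence among its sections.

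A reader might also infer more than the documents support:

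- *That every subject must stop.* Section 3.5.1 bars additional entries; it does not clearly cover subjects already treated beyond progression.
- *That any small new lesion forces a stop.* Appendix 3, Section 3.3 uses small size as its example of an equivocal lesion, for which therapy continues until follow-up clarifies it.
- *That about 10% of subjects are affected.* The figures in Sections 1.4.14 and 1.4.15 come from other studies and have different denominators. They describe progression preceding benefit, not how often this conflict would arise.
- *That the synopsis sets a third rule.* It omits a qualifier; it does not say that unconfirmed irPD requires stopping.

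**Conclusion.** The protocol is wrong as written. For a Part 1 or 2 subject not already in treatment beyond progression, a first, unconfirmed irPD scan calls for a stop under Section 3.5.1 and another cycle under Sections 3.1.1 and 3.1.2, while Section 3.5 requires no stop. An unequivocal new lesion with tumor burden up by less than 20% does the same, but only if Section 3.5.1 means RECIST v1.1.

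The size per subject is about 2 nivolumab and 1 lirilumab doses, rising to 4 and 2, with matching shifts in exposure and the safety window. The number of subjects is unknown and could be zero: it needs Part 1 or 2 subjects on treatment after 08-May-2018 whose first progression came after that date. The wording conflict is certain; its practical reach is not. A reader might infer that the response or PFS results are compromised; the SAP definitions do not support that.

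**What to change.** Reconcile the passages. State one progression trigger for Part 1 and 2 subjects still on treatment under Revised Protocol 12, naming the criteria (RECIST v1.1 or irRECIST) and whether confirmation is needed. Use the same wording in Protocol Sections 3.5.1, 3.1.1, 3.1.2 and 3.5, synopsis item (c), and SAP Sections 2.1.1 and 2.1.2. In Section 3.5.1, make the retained irRECIST paragraph agree with the new sentences, and say how subjects already in treatment beyond progression are handled. Which rule applies is a clinical decision for the sponsor; no view is taken here.

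The cost is a wording change and a letter to sites, with no new data or procedures.
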